**NCT Number: NCT03925220**

**Statistical Analysis Plan**

**Document Date: August 10, 2023; Revised: November 11, 2018**

## **Data Analysis Plan**

The scientific rigor of this application is reflected in our preliminary analyses, missing data detection and correction procedures, and our data analytic strategies. First, all forms will be checked for missing data and outliers prior to data entry. Attrition effects will be evaluated by testing whether systematic differences exist between participants who complete the research versus those who drop out. We will also examine any pre-existing differences between the two conditions in demographic composition and all measures collected at baseline. Pre-existing group differences in these variables will be accounted for in subsequent analyses, using baseline scores as covariates. Participants will be included in the analysis if they are randomized (i.e., intention -to-treat).

Participants who are lost to follow-up or drop out can affect the validity of the group comparisons if: 1) the outcome of interest is related to being lost or dropped, and 2) it is differential between groups. The missing data mechanism will be formally tested to determine whether it is Missing Completely at Random (MCAR) or Missing at Random (MAR). For completeness in assessing the effect of missingness, two additional analyses will be conducted: 1) a 'per-protocol' analysis among participants who complete all follow-up surveys; and 2) multiple imputation of five data sets using a discriminant function for binary outcomes and Markov chain Monte Carlo for continuous outcomes, assuming the missing data mechanism is MAR.

**Aim 1:** To determine the efficacy of the brief intervention on parent outcomes. The proportion of parents who more frequently communicate will be compared between conditions across the follow-up periods using a repeated measures log-binomial regression analysis (via generalized estimating equations; GEE), with an appropriate covariance structure and adjusting for baseline scores. Covariates will be added to the modeled analyses if differences among baseline characteristics are observed. A test for interaction between condition and follow-up point using the above models will assess whether there is a differential intervention effect across time, taking intervention dose delivered and received into account. To assess quality of mealtime interactions, we will first score the videos according to the IFIRS and then analyze the data using repeated measures analysis of covariance (i.e., a linear mixed model) to compare the two conditions across the follow-ups, using an appropriate covariance structure and adjusting for baseline scores. A similar analysis will be used for the summed scores from the FAsTask, which assess the quality of parent-child conversations about SU.

**Aim 2:** To examine the effects of the intervention on child SU beliefs, intentions, and willingness, and affiliation with substance-using peers. We will compare the proportion of children with intentions and willingness to use substances, negative SU attitudes and expectancies, and substance-using peers between conditions across the follow-up periods using a repeated measures log-binomial regression analysis (via GEE), with an appropriate covariance structure and adjusting for baseline scores.

**Secondary Aim 1:** To examine the effects of the intervention on SU initiation. To assess whether children of parents in the intervention condition delay the initiation of SU longer than the comparison condition, we will compare the incidence of initiation using a

discrete-time survival analysis via a complementary log-log regression model, as the date of initiation between follow-up time points may not be known exactly.

Exploratory analyses will be run by race and ethnicity. Because it is known that subgroup analyses have less statistical power than the primary analysis, we will conduct exploratory analyses to determine whether the efficacy of the intervention varies by race and ethnicity, to inform future adaptations.

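### The planned MCAR-or-MAR test cannot determine the missing-data mechanism, and no planned analysis covers outcome-related, arm-differential loss when the outcome is unseen

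*SAP*

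**What the plan says.** The SAP's Data Analysis Plan says that loss to follow-up threatens the group comparison if "the outcome of interest is related to being lost or dropped" and "it is differential between groups". It then plans a formal test: "The missing data mechanism will be formally tested to determine whether it is Missing Completely at Random (MCAR) or Missing at Random (MAR"). No test is named, and MNAR is not among the possible answers.

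Two additional analyses follow. One, labelled per-protocol, is an "analysis among participants who complete all follow-up surveys". The other is "multiple imputation of five data sets", "assuming the missing data mechanism is MAR". The SAP also plans to compare completers with dropouts and to include everyone randomized.

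The main models are log-binomial GEE for the binary outcomes (for Aim 2, "analysis (via GEE), with an appropriate covariance structure and adjusting for baseline scores") and, for meal and conversation quality, a "repeated measures analysis of covariance (i.e., a linear mixed model"). No weighting for missingness is stated for the GEE. Nothing in the protocol or SAP text mentions MNAR, delta adjustment, tipping points, pattern-mixture or selection models, or bounds.

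**The concern.** There are two linked faults.

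1. **The test is given a job it cannot do.** Rejection shows that missingness is related to something observed. It does not show that, given what is observed, missingness is unrelated to what is not. Non-rejection does not prove MCAR. MAR and MNAR can fit the same observed data equally well.

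2. **The plan names a threat and then analyses only part of it.** Loss that is explained by arm, baseline or earlier responses can be handled by the mixed model, or by an imputation that includes those variables. Loss driven by the answer that was never given cannot.

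If such loss differs between arms, it can create an apparent benefit or hide a real one. The documents do not show which direction, if either, is likely. The reader of the results would need to know how much of it each conclusion could withstand, and nothing planned reports that.

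**Working it through.** **Inputs.** From the protocol: at most 750 dyads (section 5.2, Sample Size) and follow-up at 3, 6, 12 and 18 months. No allocation ratio, dropout rate, alpha or event rate is given. Assumed throughout: 1:1 allocation, so 750/2 = 375 per arm, and a two-sided 0.05 level. There is no figure in the plan to reproduce.

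**Step 1. What each analysis needs.**

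| Planned analysis | Requirement | Covers arm-differential loss driven by the unseen outcome? |
|---|---|---|
| Completer vs dropout comparison | Uses observed data only | No |
| Linear mixed model | MAR | No |
| Unweighted GEE | In general more than MAR | No |
| Completers (per-protocol) | Broadly MCAR or covariate-dependent loss | No |
| Multiple imputation | MAR, as stated | No |

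**Step 2. What the test would see.** Take one visit, true risk p = 0.20 in both arms and loss d = 0.20 in both. Loss is random in the comparison arm. In the intervention arm it is k = 2 times as likely in outcome-positive children.
- Loss if negative: d/(pk + 1 − p) = 0.20/1.20 = 0.167. Loss if positive: 0.333.
- Observed risk: 0.20 × (1 − 0.333)/(1 − 0.20) = 0.167, so the risk ratio is 0.167/0.20 = 0.83 when the truth is 1.00.
- In 1,500 simulated trials, a test of missingness against arm and baseline rejects MCAR in 4.5% of runs when baseline is unrelated to outcome, which is its nominal rate. It rejects in about 9% when baseline has an odds ratio of 3 for the outcome. In both cases the imputed difference is about −3.2 percentage points, although the true difference is zero.

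**Step 3. Four visits with the planned Aim 2 model.** Assumed: prevalence 15%, no true effect, latent correlation 0.5 or 0.7, and loss odds 2 or 3 times higher for the current unseen outcome in one arm. The other arm is lost at random at the same overall rate. The GEE is log-binomial with exchangeable correlation and terms for visit, baseline and arm. The results are large-sample limits.

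| Permanent dropout, 10-30% by 18 months | GEE | MAR imputation | Completers |
|---|---|---|---|
| Intervention arm affected | 0.89-0.98 | 0.89-0.98 | 0.85-0.97 |
| Example: OR 3, 20%, correlation 0.5 | 0.926 | 0.925 | 0.900 |

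With the comparison arm affected, the GEE gives 1.02-1.13. At 20% dropout, 375 per arm and correlation 0.6 (3,000 simulated trials per setting), the false-positive rate is 6.8% for OR 2 and 9.7% for OR 3, against about 5% without MNAR loss.

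If 10-30% of visits are instead missed intermittently, each miss driven by that visit's outcome, the error is larger: GEE 0.73-0.96, completers 0.57-0.90 (intervention arm affected).

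**Step 4. Can the spread among the three analyses identify MNAR?** The largest gap in risk ratio is 0.01-0.07 under MNAR dropout and 0.02-0.13 under MAR dropout. The ranges overlap, so it cannot.

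**Step 5. What a tipping-point analysis would report.** With 20% missing, n = 375 × 0.8 = 300 per arm.
- *Continuous, observed difference 0.25 SD.* Shift = (0.25 − 1.96 × √(2/300))/0.20 = (0.25 − 0.160)/0.20 = 0.45 SD. At 10% and 30% missing it is 0.99 and 0.26 SD.
- *Binary, observed 20% vs 30%.* On the log risk-ratio scale, SE = √(0.8/60 + 0.7/90) = 0.145. Significance is lost when the risk ratio rises to exp(−1.96 × 0.145) = 0.752, an intervention risk of 0.2257. Solving 0.8 × 0.20 + 0.2 × 0.20 × k = 0.2257 gives k = 1.64, or about 1.73 if the SE is updated. On the risk-difference scale, k is about 1.74-1.78.

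**Step 6. Five imputations.** Set the limiting total variance to 1, with between-imputation share B = FMI of 0.2-0.4 and W = 1 − B. The pooled estimate varies with variance B/m, T = W + (1 + 1/m)B̂, and degrees of freedom are Barnard-Rubin with complete-data df 700. A result with limiting p = 0.021 crosses 0.05 in about 16-34% of re-imputations with m = 5, in 7% or fewer with m = 20, and in under 1% with m = 50.

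**The case against.** The strongest reply is that MAR-based main models with a completer analysis and imputation are common practice, and that the trial works to limit loss. The protocol provides re-contact for missing data, a shortened survey, and use of all data given before withdrawal. The SAP already compares completers with dropouts. These measures bear on how likely serious loss is, but none of them analyses the loss that remains.

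Several objections to stronger readings do stand:
- **The missed-visit figures should not carry the point.** The SAP speaks of participants lost or dropped, which matches permanent dropout. The larger errors come from an assumed intermittent mechanism in one arm.
- **A reader might infer that the three analyses would always agree and so reassure falsely.** That holds roughly for permanent dropout. For missed visits, completers stand visibly apart (0.69 vs 0.81 at OR 3, 20%, correlation 0.5). Such a gap would still not identify MNAR. Nor does the SAP say that agreement will be taken as proof of robustness.
- **The unweighted GEE is not a practical defect under MAR dropout.** In the same set-up its limit is 0.997-1.003.
- **Close agreement of GEE and imputation depends on the imputation model.** The SAP does not list its variables, and correlated auxiliary outcomes could separate the two.

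**Conclusion.** The point holds on logic alone: the test cannot do what the SAP says it will, and the threat the SAP names is left unexamined when the outcome is unseen. No assumed number is needed for that.

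The size in this trial is unknown. Under the dropout assumptions of Step 3 the error is modest: a null reads as a risk ratio of 0.89-0.98 or 1.02-1.13, with false positives of about 7-10% at 20% loss. It is close to nil at the mild end. These cases assume outcome-related loss in one arm only.

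A reader might infer that the trial is biased towards benefit or that its main models are invalid. The documents support neither, since they give no attrition rate and no mechanism. The imputation count is secondary. It affects only the additional imputation analysis, not the primary p-value.

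This should be corrected, but it does not overturn the primary analysis.

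**What to change.** 1. State that the test can only reject MCAR, and that it will not be used to choose or justify the MAR analyses. Extend the planned completer-versus-dropout comparison to report loss by arm and by prior outcome.
2. Add a delta-adjusted (tipping-point) imputation for each primary outcome. Shift the imputed values by arm and in both directions, on the log-odds scale for binary outcomes and in SD units for the meal and conversation scores. Report the smallest shift that changes the conclusion, and state the test scale and how the shift applies across visits.
3. Secondary: raise the imputations from 5 to about 50. Twenty would already remove most of the instability.

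The cost is SAP wording and some computing, with no new data. The downside is that a positive result may look less robust.

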5.2 Sample Size

PHASE 1:

The number of participants from each school will depend upon the number willing and available to participate in each school district, and the total number of participants from all sites combined shall not exceed 1500 (750 parent/child dyads). Note: Sometimes

participants are referred to as parent/child dyads in participant facing materials, but all verbal communication clarifies that a parent/child dyad or pair consists of 2 participants.

PHASE 2:

We will not recruit any new participants for this portion of the study.

Procedures Involved:

PHASE 1:

Eligible, consenting parents and their assenting child will complete baseline assessments related to their family practice of eating meals together, communication skills, parenting styles, and their own substance use. Parents will then be randomly assigned to one of two conditions: 1) intervention, or 2) comparison. Parents and children will then be followed at four follow-up points at 3, 6, 12, and 18 months.

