Participants that do not complete the surveys or videos within the given time period will be followed up with and asked to provide missing data. If changes are made to survey instruments after participants have already received the instrument, study staff will treat this as missing data and will contact participants to obtain the missing data.

A set of questions related to participants' experiences during the COVID-19 pandemic (March 2020-April 2021) will be appended to the end of all currently enrolled participants' next timepoint survey [as of approval from IRB from this submission on 27 Sep 2021]. Both parent and child will be asked to complete questions (6 and 2 additional questions, respectively). Participants have the option to skip any questions they do not feel comfortable responding to. The questions will only be asked once.

In situations where participants express interest in continuing with the study but lack time to complete materials for a specific time point, participants will have the option to complete a shortened survey. They will specifically consent/assent to taking this shortened survey and receiving a \$5 (3- or 6-month) or \$10 (12- or 18-month) Amazon e-gift card. This consent/assent process is completed at the beginning of the shortened survey.

The expected duration of the study is 5 years.

When a participant completes the study, we will complete the following steps:

- Offer the other group's materials to be emailed or mailed to them
- Send them the completion email and request a response to confirm their acknowledgement of completion
- Send them instructions on what to do with the tablet
- Ask them to complete a form which asks for consent to keep their contact information if they have not already completed this form at a previous timepoint

(participants may complete this form at any point during the study) for potential future studies

We will keep all contact information of adult participants for future study purposes who consent to us keeping their information for this purpose. This contact information will be kept in its own Box folder, separate from any data or other study-related files. For those that do not consent to us keeping their contact information, we will delete their contact information after five years after the cessation of the study as per the protocol (Section 17.0 Data Management and Confidentiality).

PHASE 2:

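### Discriminant-function imputation with only five data sets is a weak missing-data check for the binary outcomes: it can bias uncommon ones, and it leaves borderline results to the random seed

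*SAP*

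**What the plan says.** The SAP's Data Analysis Plan includes all randomised participants in the main analysis. It then adds two missing-data analyses: "For completeness in assessing the effect of missingness, two additional analyses will be conducted". The first is restricted to participants who complete every follow-up survey. The second is "multiple imputation of five data sets using a discriminant function for binary outcomes and Markov chain Monte Carlo for continuous outcomes", carried out "assuming the missing data mechanism is MAR".

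The binary outcomes are parent communication frequency (Aim 1) and the five child outcomes of Aim 2: "We will compare the proportion of children with intentions and willingness to use substances, negative SU attitudes and expectancies, and substance-using peers between conditions". Both aims use a "repeated measures log-binomial regression analysis (via GEE), with an appropriate covariance structure and adjusting for baseline scores" or its equivalent. Mealtime interaction quality and the FAsTask scores are analysed by linear mixed models.

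The SAP does not state the variables in the imputation model, a seed, a reason for five data sets, or what follows if the imputed and main results differ. Neither document gives expected attrition or outcome prevalence.

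**The concern.** There are two separate weaknesses.

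**Imputation model.** The discriminant method turns a normal-theory classification rule into a probability and draws the missing value from it. Natural predictors of a missing yes/no answer are arm and the same answer at other waves, all of them binary. Within an outcome class a binary predictor is not normal, and its variance changes with its mean, so the common-covariance assumption fails too. The error is largest when the outcome is uncommon, as intentions and willingness may be in grades 5–7. It carries into the arm comparison when the arms lose different kinds of children. The SAP itself names that threat: loss that is related to the outcome and unequal between groups.

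**Number of data sets.** With five, the pooled estimate and its standard error both carry simulation noise. No seed is fixed in advance.

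Unweighted GEE is not generally valid under MAR when dropout depends on earlier outcomes outside the model, and the other check uses completers only. For the GEE-analysed outcomes, multiple imputation is therefore the one planned analysis designed for MAR. If it is unreliable, the plan has no sound test of whether dropout explains a finding.

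**Working it through.** The SAP gives no derivation for five data sets, so there is no figure to reproduce. From the documents: m = 5, the discriminant method, MAR, and a ceiling on size ("the total number of participants from all sites combined shall not exceed 1500 (750 parent/child dyads"). Assumed: prevalence, association between waves, dropout, 1:1 allocation and two-sided 0.05.

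**1. Imputation probability with one binary predictor x (the earlier answer).** Let π be prevalence now, and m1 and m0 the probability of an earlier positive among those now positive and now negative.

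- s² = π·m1(1−m1) + (1−π)·m0(1−m0)
- logit P(1|x) = ln[π/(1−π)] + (m1−m0)x/s² − (m1²−m0²)/(2s²)

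Take π = 0.10, m1 = 0.60, m0 = 0.05. Then s² = 0.024 + 0.04275 = 0.06675.

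- x = 1: −2.197 + 8.240 − 2.678 = 3.365, so 96.7%. Bayes gives 0.06/0.105 = 57.1%.
- x = 0: −2.197 − 2.678 = −4.875, so 0.8%. Bayes gives 0.04/0.895 = 4.5%.

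With a weaker association (m1 = 0.40, m0 = 0.07), an earlier positive gets 70% against a true 39%.

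**2. Effect on the arm comparison when there is no true effect.** Assumed dropout: arm A loses 50% after a positive wave and 15% after a negative one; arm B loses 25% and 20%. True prevalence is 10% in both arms, and 10.5% were positive earlier. Observed values keep the true probabilities; missing values take those of step 1.

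- A: 0.105(0.5×0.571 + 0.5×0.967) + 0.895(0.85×0.0447 + 0.15×0.0076) = 0.116
- B: 0.105(0.75×0.571 + 0.25×0.967) + 0.895(0.80×0.0447 + 0.20×0.0076) = 0.104
- RR = 0.1158/0.1037 = 1.12 (truth 1.00)

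Correct conditional probabilities, which logistic imputation recovers here, return 0.100 in both arms. Equal dropout gives RR = 1.00 even with the discriminant rule. At π = 0.30, m1 = 0.60, m0 = 0.20, the rule gives 61% and 15% (truth 56% and 18%). The arms become 0.3055 and 0.3007, RR 1.02. With m1 = 0.70 and m0 = 0.15 the RR is 1.03, or 1.04 when the rule is fitted to the observed cases with arm as a predictor. Across the structures examined, RR ran from about 1.03 to 1.12 at 10% prevalence.

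In simulations with 375 per arm, dropout after a positive wave of 30% vs 10% (after a negative wave 4% vs 6%) gave RR 1.07–1.09 and two-sided false rejection of 8–9% against 5%. At 20% vs 15% the bias was about 0.02 in log RR, with 4.7% rejection.

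**3. Effect when there is a true effect and missingness is driven mainly by baseline covariates.** The discriminant function pulled the RR toward 1. Its excess error in log RR over logistic imputation was about 0.01 at a 30% control rate (SE 0.15), 0.05 at 10% (SE 0.29) and 0.075 at 5% (SE 0.47), so at most about 0.2 SE. Coverage was 0.92–0.96 for both methods.

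**4. Monte Carlo error of the pooled estimate**, in standard errors: √[(FMI/m)/(1+FMI/m)], where FMI is the fraction of missing information.

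| FMI | m = 5 | m = 50 |
|---|---|---|
| 0.2 | √(0.04/1.04) = 0.20 | √(0.004/1.004) = 0.06 |
| 0.3 | √(0.06/1.06) = 0.24 | √(0.006/1.006) = 0.08 |

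**5. Disagreement about p < 0.05 between two runs on the same data.** Here T = W + (1+1/m)B, with B drawn as a scaled chi-square on m−1 df and a t reference on Rubin's df. At an infinite-imputation z of 2.2, five-set runs disagree in 38% (FMI 0.2) and 45% (FMI 0.3) of cases; 50-set runs disagree in 0.2–0.3% and 2%. At z = 2.8, five-set disagreement falls to 2% and 9%.

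Re-imputing fixed simulated data agrees. A set with p = 0.041 at m = 200 gave p from 0.016 to 0.132 (5th to 95th percentile) at m = 5, and 0.028 to 0.053 at m = 50. A set with p = 0.009 stayed below 0.05 in 95% of five-set reruns, and one with p = 0.12 fell below it in 4%.

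**The case against.** The strongest reply is that this analysis is supplementary, no decision rule uses its p-value, and the main GEE and mixed-model results do not change. That is correct and limits the severity. A second reply is that the bias needs outcome-related dropout that differs by arm, mainly with low prevalence, and that every such figure is assumed. That also stands: with equal dropout there was no material bias. Nor does the SAP list the imputation variables, so binary earlier waves as predictors are the natural reading, not a stated fact.

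Four stronger readings are tempting but unsupported.

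- **That the method necessarily adds bias, or that its verdict always turns on the seed.** Both are conditional, as the working shows.
- **That gaps will be intermittent and so defeat a one-variable model.** The protocol's account of families who "express interest in continuing with the study but lack time to complete materials for a specific time point" offers them a shortened survey, which Section 10.0 describes by name as limited to the specific aims, and staff will chase missing data. These are measures against gaps. Chained equations are themselves built from one-variable models, so the objection would not separate the methods.
- **That this is the only MAR analysis in the plan.** The mixed models for the continuous outcomes are likelihood-based and already handle MAR.
- **That it lies further from the truth than available-data GEE.** This depends on the scenario. In one simulation GEE across waves was close to 1.00. In step 2, available data at the later wave alone give 0.0787/0.0969 = 0.81, so there the discriminant rule over-corrects.

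**Conclusion.** The point holds in conditional form. The SAP names a method whose assumptions binary predictors cannot meet, and a number of data sets too small to settle a borderline result. The possible bias in the RR is about 3–12% at 10% prevalence and 1–2% at 30% (up to 4% with strong persistence) when outcome-related dropout differs by arm, and nil when it does not. The seed matters for results near the threshold and seldom for clear ones. These sizes rest on assumed prevalence, persistence and dropout. What does not rest on them is that the check is weakest in the situation it is meant to examine, and that no other planned analysis of the six GEE-analysed outcomes is built for MAR. The primary results stand as planned, so this is a worthwhile improvement and not a threat to the trial's main conclusions.

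**What to change.** Replace the imputation sentence with: Missing outcomes will be imputed by chained equations, with logistic regression for binary outcomes and linear regression or predictive mean matching for continuous outcomes; each model will include arm, the baseline value and all other waves of the same outcome; 50 data sets will be created with a recorded seed.

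Fifty exceeds the rule of thumb of 100 × FMI for FMI up to 0.5. Logistic imputation is not exact when effects are multiplicative on risk: in step 3 it left an error of 0.00 to 0.04 in log RR, but this was never larger than the discriminant function's. The cost is one SAP sentence and minutes of computing, with no new data.
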